## 5.7 Primary and Secondary Analysis

### 5.7.1 General Considerations

The FAS/SAS will be used for the analysis of the primary and secondary endpoints. Analyses of the secondary endpoints will be repeated on the Per Protocol (PP) Set if ≥10% of participants are excluded from the FAS/SAS Set.

All analyses will be performed overall and by treatment regimen (chronic treatment only, flare-up treatment only, chronic and flare-up treatment).

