9.4.3 Analysis of Secondary Endpoints

Data related to the secondary endpoints will be included in the participant data listings using the FAS/Safety Set. Secondary endpoint analyses and summary tables will be presented by parent study, by palovarotene status at the time of transition to Study CLIN-60120-452 and treatment regimen and overall for the FAS/Safety Set.

Analyses of the secondary endpoints will be repeated on the Per Protocol (PP) Set if $\geq 10\%$ of participants are excluded from the FAS/Safety Set.

Data will be tabulated descriptively, i.e. the number and percentage of participants for each category for categorical parameters, and the number, mean, SD, 95% CIs of the mean/median, median, minimum and maximum for continuous parameters will be tabulated.

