## 4 ANALYSIS SETS

For the purposes of analysis, the following analysis sets are defined:

Participant Analysis Set	Description
Screened Set	All participants who signed the ICF
Enrolled Set	The Enrolled Set will contain all participants who were assigned to receive palovarotene in Study CLIN-60120-452. Participants will be included based upon the "Is participant included in the study?" question within the eCRF.
Full Analysis Set (FAS)/Safety Analysis Set (SAS)	The FAS/SAS will contain all participants who received at least one dose of palovarotene during Study CLIN-60120-452.
Per Protocol (PP) Set	The PP set will contain all participants from the FAS who did not experience any major protocol deviations that may interfere with safety/efficacy evaluations. Please refer to section 5.3 for details regarding the management of deviations.

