## 5.2 Disposition and Analysis Sets

The following disposition summaries and listings will be provided:

- Summary table with the number and percentages of enrolled participants per country, site on the screened set
- Summary table with the number and percentage of participants screened, enrolled, treated, completed, withdrawn and reason for withdrawal on the screened set
- Summary table with the number and percentage of participants per visit on the enrolled set
- Summary table on duration of participant participation in the study on the enrolled set. The definition of the duration of participant participation is from date of consent to the last study visit or date of completion/discontinuation, whichever comes later.
- Listing of dates of visit including duration of participant participation
- Listing of withdrawal participants

In addition, the below summaries and listings will be provided:

- Summary of the number of participants within each treatment regimen subgroup
- Summary of the number and percentages of participants included in each analysis set with reasons for exclusion from each analysis set
- Listing including flag for each analysis set and reason for exclusion from each set

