## 5.3 Protocol Deviations

An exhaustive list of major/important protocol deviations that may occur during the course of the study and any action to be taken regarding exclusion of participants from the PP set is defined in Protocol Deviation Plan. Major protocol deviations will be determined and finalised during the data review for the final analysis and documented.

The following protocol deviation summary and listing will be provided on the enrolled set:

- Number and percentage of participants with major protocol deviations by deviation category
- A listing of major protocol deviations.
- A listing of all protocol deviations

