#### **5.4 Demography and Other baseline characteristics**

All demographic and baseline characteristics summaries and listings will be provided for the FAS/SAS. The summary will be repeated on the PP set if  $\geq 10\%$  of participants are excluded from the FAS/SAS. [Note: Demographic variables of age and sex will be collected in Study CLIN-60120-452, all other variables will be transferred from the parent study database]

Following descriptive summaries will be provided:

- Demographic variables (age, age categories [ $<15$ ,  $15-25$  &  $>25$ ] and EudraCT age categories, sex, race, ethnicity, height (cm), weight (kg) and BMI ( $\text{kg}/\text{m}^2$ )). See appendix A6 for defined EudraCT age categories
- Disease history (time since date of diagnosis by a physician (years), method of diagnosis and type of FOP genetic mutation)
- Flare-up history over the past 12 months prior to the Inclusion Visit (number of flare-ups, start and stop date of flare-ups, location of flare-ups, symptoms of flare-up, cause of flare-up and time since last flare-up (months)).
- Extra bone growth history over the past 6 months prior to the Inclusion visit (number of extra bone growths, locations, preceded by and symptoms)
- Bone maturity history, for participants aged  $<18$  years at study inclusion, (bone age, difference between chronological age and bone age (months), hand/wrist and knee epiphyseal assessment and skeletally mature assessments)

Time since date of diagnosis is defined as (Date of the first IMP administration of palovarotene in Study CLIN-60120-452 - date of diagnosis).

Date of diagnosis is collected directly for study PVO-1A-301. For PVO-1A-202/PVO-1A-204, age at first confirmation of heterotopic ossification (years) will be considered equivalent to the age of diagnosis and as such in combination with the birth date used to derive the year of the equivalent date of diagnosis.

[Note: 1 year = 365.25 days and 1 month = 30.4375 days].

Difference between chronological age and bone age is defined as (bone age – estimated age at time of bone maturity assessment [age captured at the inclusion visit will be used to calculate the year of birth, from which age at time of bone maturity assessment will be estimated by imputing the day and month as 30th June]).

Listings will also be provided for all the summaries listed above.

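### The trigger for the Per Protocol repeat names the FAS/SAS instead of the PP Set and gives no denominator, so as written it ignores major deviations (modest impact, easily fixed)

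*SAP*

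**What the plan says.** SAP section 4 defines the two sets. For the first: "The FAS/SAS will contain all participants who received at least one dose of palovarotene during Study CLIN-60120-452". For the second: "The PP set will contain all participants from the FAS who did not experience any major protocol deviations", limited to deviations that may interfere with the safety or efficacy evaluations. Protocol 9.3 gives the same definitions.

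The repeat on the PP Set depends on a 10% threshold, stated in three places:

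- SAP 5.7.1, secondary endpoints: at least 10% of "participants are excluded from the FAS/SAS Set".
- SAP 5.4, demographic and baseline summary: at least 10% "of participants are excluded from the FAS/SAS".
- Protocol 9.4.3, secondary endpoints: at least 10% "of participants are excluded from the FAS/Safety Set".

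None of the three says what the percentage is taken of. SAP 2.6, which lists changes from the protocol's statistical section, does not mention the rule.

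**The concern.** The condition and the analysis it controls refer to different things. What separates the PP Set from the FAS/SAS is major deviations. What separates the FAS/SAS from the enrolled or screened participants is whether a dose was taken. A threshold on exclusion from the FAS/SAS therefore says nothing about how far the PP Set differs from the FAS/SAS, which is the only reason to run the repeat.

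The PP repeat is the only planned re-analysis of the secondary endpoints without major deviators. SAP 5.3 otherwise provides counts and listings of deviations, and it finalises major deviations at the data review for the final analysis. If the rule is settled only then, when the number of deviators is known, a prespecified decision becomes a choice made after seeing the data. Two programmers could also reasonably deliver different table packages from the same text.

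**Working it through.** **Inputs.** Maximum enrolment is 87 (SAP 2.3). The set definitions are in SAP 4. Day 1 is both the Inclusion Visit and the first administration (protocol 9.4.1). The proportion enrolled but never dosed is not given, so a range of 0% to 10% is assumed below. There is no sample size or power figure to reproduce, because the study has no formal calculation.

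**Step 1: what exclusion from a set means in this SAP.** SAP 5.2 plans a table of the "number and percentages of participants included in each analysis set with reasons for exclusion from each analysis set", so exclusion from a set means not being a member of it. SAP 5.3 says that "any action to be taken regarding exclusion of participants from the PP set is defined in Protocol Deviation Plan". When the SAP means exclusion because of deviations, it names the PP set. The trigger names a different set.

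**Step 2: the literal rule against a PP-based rule.** Let u be the number enrolled but undosed and d the number of dosed participants whose deviations exclude them from the PP Set. With an enrolled denominator, the literal rule fires if u/87 ≥ 0.10. Since 0.10 × 87 = 8.7, that needs u ≥ 9. The PP-based rule fires if d/(87 − u) ≥ 0.10.

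| u | FAS/SAS | d | Literal: u/87 | PP-based: d/(87 − u) |
|---|---|---|---|---|
| 0 | 87 | 8 | 0%, no | 9.2%, no |
| 0 | 87 | 9 | 0%, no | 10.3%, yes |
| 0 | 87 | 40 | 0%, no | 46.0%, yes |
| 0 | 87 | 87 | 0%, no | 100%, yes |
| 8 | 79 | 8 | 9.2%, no | 10.1%, yes |
| 9 | 78 | 0 | 10.3%, yes | 0%, no |

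The literal column does not depend on d. In the last row the rule orders a repeat on a PP Set identical to the FAS.

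**Step 3: how often the literal rule would fire.** Treat the number undosed as Binomial(87, p), with p assumed. The chance of 9 or more is:

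| p | 0% | 1% | 2% | 3% | 5% | 8% | 10% |
|---|---|---|---|---|---|---|---|
| P(at least 9) | 0 | <0.0001 | 0.0001 | 0.001 | 0.030 | 0.26 | 0.51 |

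The answer runs from never to about one time in two, depending on a rate the documents do not supply.

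**Step 4: the denominator.** If the percentage is of the FAS/SAS itself, the proportion excluded from it is 0 by definition and the rule can never fire. If it is of the Screened Set (all who signed consent), screen failures count as well. With 87 enrolled and all dosed, 10 screen failures would be enough (10/97 = 10.3%; 9/96 = 9.4% is not). Under every choice, deviations stay outside the rule.

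**The case against.** The strongest reply is that the intent is plain. The PP Set is built by dropping participants from the FAS, so the clause can be taken as 10% of the FAS being dropped to form the PP Set. The literal reading defeats itself, as the last row of the first table shows, and a study team might never apply it. This largely stands as an account of intent. It does not make the text say so: SAP 5.2 and 5.3 use the phrase in the other sense, and the denominator is still missing.

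A reader might infer that the PP analysis would almost never run. The documents do not support that. First dosing on Day 1 makes a low undosed rate plausible, but no rate is stated. SAP 5.1.1.2 provides a Not Treated group for outputs that do not use the FAS/SAS. With a Screened Set denominator, screen failures could fire the rule.

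A reader might also take three appearances of the clause as proof that it is deliberate. Copied wording repeats one slip and shows nothing about intent.

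The impact is also limited. The study is noncomparative and descriptive, the primary endpoint is analysed on the FAS/SAS with no PP repeat planned, and deviations would be visible in the tables and listings of SAP 5.2 and 5.3. That stands, though counts and listings do not replace PP summaries.

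**Conclusion.** The rule is wrong as written, with modest impact. On the documents' own definitions, major deviations never enter the trigger for the PP repeat, and the denominator is not named. With 87 enrolled and all dosed, the literal rule would not fire for any number of deviators; with 9 undosed and none deviating, it would fire to no purpose. These two statements rest only on the set definitions, enrolment at the maximum of 87 and, for the second, an enrolled denominator. How often the rule would misfire in practice cannot be stated.

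The probable intent is exclusion from the PP Set, so this is a defective decision rule that a team may well read correctly, not a demonstrated loss of the PP analysis. The effect is confined to the descriptive secondary-endpoint tables and the baseline summary. It should be corrected because following the text gives the wrong answer and the correction costs almost nothing.

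**What to change.** In SAP 5.4 and 5.7.1, replace the condition with: *repeated on the PP Set if ≥10% of FAS/SAS participants are excluded from the PP Set*. This names both the set and the denominator. It fires at 9 participants when the FAS/SAS is 87 (9/87 = 10.3%; 8/87 = 9.2% does not fire).

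Record it in SAP 2.6 as a change from protocol 9.4.3, before database lock. That is enough; a protocol amendment for this clause alone is not needed.

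The cost is one phrase in two sections, one entry in SAP 2.6 and, if the threshold is met, one extra set of descriptive tables. Data collection, participant management and the primary analysis do not change.

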#### 5.7.1.1 Significance Testing and Estimations

The statistical analysis is only descriptive therefore no formal statistical significance testing will be performed.

#### 5.7.1.2 Handling of Dropouts and missing data

Diligent attempts will be made to limit the amount of missing data and to follow-up all enrolled participants to collect the primary and secondary efficacy endpoints for the statistical analysis.

With the exception of the QoL questionnaires, where missing data will be handled based upon the calculation of the derived scores, missing data will not be replaced but will be displayed in all relevant tables.

#### 5.7.1.3 Statistical/analytical issues

Given all analysis is descriptive, adjustment for multiplicity is not applicable to this study.

## 5.7.2 Analysis of Primary Endpoint

### 5.7.2.1 Endpoints

The primary endpoints of the study are:

- Incidence and description of all treatment emergent adverse events (TEAEs) whether or not they are considered as related to the study intervention;
- Incidence and description of all serious and nonserious treatment-related TEAEs;
- Incidence and description of all serious TEAEs, whether or not they are considered as related to the study intervention;
- Incidence and description of all nonserious TEAEs whether or not they are considered as related to the study intervention.

### 5.7.2.2 Primary Analysis – Adverse Events

All adverse events (AEs) recorded in the eCRF will be coded using the latest version of MedDRA dictionary at the time of the database lock and will be classified by System Organ Class (SOC) and Preferred Term (PT). [Note: All ongoing AEs at the time of participant transition will be transferred from the parent study database]

AEs will be classified as Treatment-Emergent AEs (TEAEs) according to the rules below:

- Events with start date on or after the date of first IMP administration and up to 30 days after date of last dose of treatment of palovarotene in Study CLIN-60120-452 (or date of last contact if not available).

- Ongoing AEs from the parent study with a worsening in intensity or relationship (see relationship and intensity order below) to the study intervention following transition to Study CLIN-60120-452. New AEs during Study CLIN-60120-452 will be compared by SOC and PT to all previous study ongoing AEs for comparison of the intensity and relationship.

Ongoing AEs from the parent study with no change in intensity or relationship to the study intervention following transition to Study CLIN-60120-452 will therefore be an AE (non-TEAE).

In the case where it is not possible to define an AE as treatment emergent or not, the AE will be classified by the most conservative case; i.e. treatment emergent.

The below summaries will be provided:

- An overview table summarising the:
  - number and percentage of participants with at least one of the following AEs: any AE; any TEAE; maximum intensity of TEAEs; causality of TEAEs, worst causality and intensity of TEAEs (worst case); TEAE leading to a dose change; TEAE leading to withdrawal; TEAE leading to death; Serious Adverse Events (SAEs); Serious TEAE;
  - corresponding number of events for each of the AE categories listed above
- A summary of the number and percentage of participants reporting an AE by SOC and PT
- A summary of the number and percentage of participants reporting a TEAE by SOC and PT
- A summary of the number and percentage of participants reporting a TEAE by maximum intensity, SOC and PT
- A summary of the number and percentage of participants reporting a TEAE by worst causality, SOC and PT
- A summary of the number and percentage of participants reporting a related TEAE by SOC and PT
- A summary of the number and percentage of participants reporting a TEAE by intensity, causality, SOC and PT
- A summary of the number and percentage of participants reporting a non-Serious TEAE by SOC and PT
- A summary of the number and percentage of participants reporting a non-Serious related TEAE by SOC and PT
- A summary of the number and percentage of participants reporting a TEAE leading to treatment discontinuation by SOC and PT
- A summary of the number and percentage of participants reporting a TEAE leading to dose change (increase or decrease) by SOC and PT

The below summaries will also be provided by treatment dose at time of AE onset (5mg, 10/20mg and all palovarotene):

- Overall summary of Adverse events
- A summary of the number and percentage of participants reporting a TEAE by SOC and PT

- A summary of the number and percentage of participants reporting a TEAE by maximum intensity, SOC and PT
- A summary of the number and percentage of participants reporting a TEAE by worst causality, SOC and PT
- A summary of the number and percentage of participants reporting a TEAE leading to treatment discontinuation by SOC and PT
- A summary of the number and percentage of participants reporting a TEAE leading to dose change (increase or decrease) by SOC and PT

To calculate the treatment regimen at time of AE onset, the start date of each AE will be merged with each participant dosing log. Given dosing end dates are not captured the latest dosing record prior to the AE start date will be identified. If the dosing record is either 0 mg or after treatment discontinuation the regimen will be set to “off treatment”.

AEs will be counted as follows:

- AEs summaries will be ordered in terms of decreasing frequency for SOC and PT within the overall column of each output.
- Participants with more than one AE within a particular SOC are counted only once for that SOC. Similarly, participants with more than one AE within a particular PT are counted only once for that PT.
- Participants reporting a TEAE more than once within that SOC/ PT, the TEAE with the worst-case intensity (intensity order: severe > missing > moderate > mild) will be used in the corresponding intensity summaries.
- Participants reporting a TEAE more than once within that SOC/ PT, the TEAE with the worst-case causality to study medication (order: related > missing > not related) will be used in the corresponding relationship summaries;
- If the intensity/relationship is missing for a TEAE, it will be considered as missing in the summary tables; Summaries by intensity/relationship will be presented (in the same order as above).
- The non-serious TEAEs table should include a specific row “any non-serious TEAE above x%”

A listing with all AEs data will be listed including non-TEAEs, Treatment-emergence status will be flagged in the listing. In addition listings for participants with a pregnancy or overdose will be presented (a table will be provided if more than 3 cases are observed in either category).

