9.4.2 Analysis of Primary Endpoint

The primary endpoint is the incidence and description of all TEAEs, serious and nonserious treatment-related TEAEs, all serious TEAEs and all nonserious TEAEs.

A TEAE is defined as any AE that occurs after signing the ICF of Study CLIN-60120-452 or an ongoing AE from the parent study with a worsening in severity or relationship to the study intervention following transition to Study CLIN-60120-452.

Ongoing AEs from the parent study with no change in severity or relationship to the study intervention following transition to Study CLIN-60120-452 will not be considered TEAEs.

Any event that first occurred during participation in the parent study and is ongoing at the time of transition to Study CLIN-60120-452 will therefore be a (non-TEAE) AE.

All ongoing AEs from the parent study and all TEAEs that occur following the signing of the ICF until last study intervention intake + 30 days will be included in the participant data listings using the Full Analysis Set (FAS)/Safety Set. Primary endpoint analyses and summary tables will be presented by parent study, by palovarotene status at the time of transition to Study CLIN-60120-452 and treatment regimen and overall for the FAS/Safety Set.

Adverse events/TEAEs will be coded according to Medical Dictionary for Regulatory Activities (MedDRA) and will be classified by PT and SOC. Adverse events/TEAE listings will be presented by participant, SOC and PT.

The incidence of all reported TEAEs, serious and nonserious treatment-related TEAEs, all serious TEAEs, all nonserious TEAEs, TEAEs leading to death and TEAEs leading to treatment discontinuation will be tabulated separately. In addition, summary tables for TEAEs will be presented by maximum intensity and study intervention relationship (investigator-reported causality assessment).

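### A carried-over AE record that turns serious or fatal on study, with intensity and causality unchanged, is not counted in the serious-TEAE primary endpoint

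*SAP*

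**What the plan says.** SAP 5.7.2.2 gives two routes to treatment emergence. The first is by date: "Events with start date on or after the date of first IMP administration and up to 30 days after date of last dose". The second is for carried-over events: "Ongoing AEs from the parent study with a worsening in intensity or relationship". It adds that "New AEs during Study CLIN-60120-452 will be compared by SOC and PT to all previous study ongoing AEs for comparison of the intensity and relationship". It then states that "Ongoing AEs from the parent study with no change in intensity or relationship to the study intervention following transition" count as AEs but not as TEAEs.

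Protocol 9.4.2 has the same second route, "an ongoing AE from the parent study with a worsening in severity or relationship to the study intervention", and the same exclusion for unchanged events. The SAP did not introduce the rule.

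One of the four primary endpoints in SAP 5.7.2.1 is "Incidence and description of all serious TEAEs, whether or not they are considered as related to the study intervention". Under the Deaths and SAEs heading, the summaries of serious events, serious related events and events leading to death all count TEAEs only. The overview table has separate rows for SAEs and for serious TEAEs, and there are listings of all SAEs and all deaths.

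Protocol 8.3.1 has AEs and SAEs that are ongoing at transition entered again in this study's eCRF when consent is signed.

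**The concern.** Seriousness and intensity are different attributes. A moderate event can lead to hospitalisation and remain moderate, and an event already graded severe has no higher grade to move to. The carried-over rule does not look at seriousness, so an event can become serious during this study and still be classed as not emerging in it.

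What is at stake is the count in a named primary endpoint. Every participant comes from a palovarotene study and ongoing events are brought forward, so the carried-over route will be used. The SAE row cannot stand in for the endpoint. It may also hold SAEs inherited unchanged from the parent study, and a reader could not separate those from events that turned serious here.

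**Working it through.** The plan states no sample size calculation or expected event count that bears on this point, so there is no figure to reproduce. The check applies the rule as written.

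**Inputs.** Worsening triggers: intensity and relationship (SAP 5.7.2.2, protocol 9.4.2). Intensity ranks: "intensity order: severe > missing > moderate > mild" (SAP 5.7.2.2). Relationship ranks, in the same section: related above missing above not related. Maximum N = 87 (SAP 2.3).

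**Rule for a carried-over record.** TEAE = (intensity rank rises) OR (relationship rank rises). Seriousness does not enter.

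**Enumeration.** Take one ongoing, nonserious parent-study record that becomes serious on study. Leave out missing values and improvements. There are 6 non-improving intensity transitions and 3 non-improving relationship transitions (NR = not related, R = related), so 6 × 3 = 18 cells.

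| Intensity | NR → NR | NR → R | R → R |
|---|---|---|---|
| mild → mild | non-TEAE | TEAE | non-TEAE |
| mild → moderate | TEAE | TEAE | TEAE |
| mild → severe | TEAE | TEAE | TEAE |
| moderate → moderate | non-TEAE | TEAE | non-TEAE |
| moderate → severe | TEAE | TEAE | TEAE |
| severe → severe | non-TEAE | TEAE | non-TEAE |

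The rule counts 12 of 18 cells and drops 3 × 2 = 6. These are cells of the rule, not event frequencies. An event already severe and already related cannot be promoted at all, whatever its outcome. If it is fatal, it also misses the table of TEAEs leading to death.

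**Does the conservative default rescue it?** That default opens with "In the case where it is not possible to define an AE as treatment emergent or not". In the six dropped cells the rule gives a definite answer, so the default is not reached.

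**Does the start-date route rescue it?** Yes, if the serious phase is entered as a new AE dated on or after first dose and within the 30-day limit. No, if the carried-over record is updated.

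**Size.** One participant moves an incidence by 1/87 = 1.15 percentage points, but only if that participant has no other serious TEAE, because each participant is counted once. As an illustration, suppose nobody else has a serious TEAE and 0 to 3 participants are affected. That range is my assumption. So is the exact (Clopper-Pearson) 95% interval, since the SAP names no method.

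- 0/87 = 0.00% (0 to 4.15)
- 1/87 = 1.15% (0.03 to 6.24)
- 2/87 = 2.30% (0.28 to 8.06)
- 3/87 = 3.45% (0.72 to 9.75)

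**After the fix.** With becoming serious added as a third trigger, all 18 cells count.

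**The case against.** The strongest reply is that the gap depends on recording practice. Protocol 10.3.3 covers the recording and follow-up of AEs, and it is not in the text available for this review. If it requires a new record when an event turns serious, the start-date route counts the event. The SAP's comparison of new AEs with ongoing ones suggests that new records are expected at least sometimes. This stands as a condition on the finding. It does not remove it, because no available passage requires a new record and the comparison itself reads only intensity and relationship.

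It is also fair to say that the events remain visible in the SAE row and the listings, that the study is descriptive with no comparator, and that any event which also worsens in intensity or causality is counted. All of this stands and limits the damage.

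A reader might be tempted by stronger readings that the documents do not support:

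- *That carried-over events which get worse are missed in general.* Twelve of the 18 cells are counted.
- *That each misclassified participant moves an incidence by at least 1.15 points.* A participant with another qualifying event moves it by 0.
- *That promoting an event on a causality upgrade alone is an error.* The protocol defines such events as TEAEs and the SAP follows it. An upgrade can reflect new information, such as recurrence after the rechallenge that protocol 7.1.4 allows. Removing these events would take protocol-defined TEAEs out of a primary endpoint.
- *That ranking missing above moderate and mild is a fault to be cured by keeping the parent value.* The ranking errs towards counting, in line with the SAP's conservative policy. Carrying the parent value forward would conflict with the stated policy of not replacing missing data (protocol 9.4.1, SAP 5.1).

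**Conclusion.** The gap is real and narrow. It affects a carried-over record that becomes serious or fatal on study while intensity and relationship stay the same. Such a record is definitively a non-TEAE under both documents, so it falls outside a primary endpoint and the tables built on it, though it is not lost from the report.

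The conclusion assumes that the site updates the carried-over record and does not open a new one. The number of such events cannot be derived from the documents, so 1.15 points is the effect of one qualifying participant at the maximum N, not an estimate of the total effect. The wording should be corrected because the rule gives the wrong count where it applies and the correction is small.

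**What to change.** In SAP 5.7.2.2, extend the worsening criterion for carried-over AEs with: *or becomes serious (including fatal) following transition to Study CLIN-60120-452*. State that *including fatal* also covers an event already serious at transition that turns fatal. Adjust the sentence on unchanged events to match, and add seriousness to the SOC/PT comparison of new with ongoing AEs. Judge the change by comparing on-study seriousness with the parent-study record; no separate date of becoming serious is then needed. Declare the departure from protocol 9.4.2 in SAP 2.6, which already records one change from the protocol. If the database is already locked, SAP section 1 sends the change to the clinical study report.

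Keep causality upgrades as TEAEs. Optionally, flag in the AE listing those promoted by relabelling alone. Leave missing intensity and relationship unimputed.

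The cost is a short edit to the definition and its programming, given that the parent-study seriousness value is available alongside the carried-over record. The downside is that serious-TEAE counts may rise slightly and will no longer follow the protocol wording exactly.
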